5.8. Statistical Method

5.8.1. Sample size calculation and justification

Based on power analysis (power=80%, see assumptions below) and the design of the study, 50 patients will be accrued to each group (n=100).

The study has a two-factor repeated-measures ANO VA design. For the power analysis, the assumption of sphericity will be made (*epsilon* = 1). Sphericity is the condition where the variances of the differences between all combinations of related groups (levels) are equal.

Assumptions and parameters of power analysis:

Sphericity: *epsilon* = 1 Type I error: *alpha* = 0.05 Type II error: *beta* = 0.2

Required power: power = 100(1 - B) = 80%Effect size: f = 0.1, 0.25, 0.33, 0.4, 0.8

Cohen's effect size for F test, 0.1 ("small"), 0.25 ("medium"), 0.33, and 0.4 ("large"). Effect

size of 0.33 was used.

5.8.2. Statistical Analysis Plan

Primary Analysis

Treatment effect on the primary dependent variable (ISMI score) will be measured by using a two-factor repeated-measures analysis of variance (ANOVA). A P value of less than 0.05 will be considered to indicate statistical significance.

Secondary Analysis

Treatment effect on the secondary dependent variables (diagnosis category) will be measured by using a two-factor repeated-measures analysis of variance (ANOVA). A P value of less than 0.05 will be considered to indicate statistical significance.

Exploratory Analysis

Treatment effect on the exploratory variable (ISMI score 3 weeks after baseline) will be measured by using a two-factor repeated-measures analysis of variance (ANOVA). A P value of less than 0.05 will be considered to indicate statistical significance.

6 - Trial Administration

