Though a rich precedent exists for utilizing recording technology in music therapy, its clinical potential and therapeutic relevance have not been systematically investigated. Kirkland & Nesbitt (2019) offer a model of therapy-oriented recording as a medium for self-reflection and personal narrative review for patients with concurrent psychiatric disorders. When framed as a mental health advocacy project to be released to the general public, recording the patient-composed song in the MTAR treatment sequence offers patients an opportunity to proactively work together in a socially supportive context to change public perception of mental illness, to refute self-relevance of stereotypes by strengthening and broadening self-concept, and empower themselves and each other with creative, expressive tools to confront and adapt to the "experience, perception, or anticipation of negative social reactions" (Livingston & Boyd, 2010) to mental illness that initiate stigma internalization.

In this study, subjects will work together with a certified music therapist (MT) in groups of 5 to 7 subjects per group to compose, rehearse, and record a song to be released to the general public for the purpose of generating anti-stigma mental health awareness. The primary objective is to reduce internalized stigma from baseline relative to the control group as measured by the 29-item Internalized Stigma of Mental Illness Inventory (ISMI; Ritsher et al., 2003). The secondary objective, examining the association between treatment effect and diagnostic category, can assist in generating hypotheses related to effective implementation. The exploratory goal of the study is to examine the potential for the treatment effect of the music therapy intervention to persist after 21 days from baseline.

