3.4. Primary Outcome Variables

ISMI score pre-treatment, ISMI score post-treatment

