4.1 General Design

This prospective clinical trial's pseudo cluster randomized controlled design (Borm et al., 2005) will take advantage of the unit's two separate residential areas ("wings", ACU West and ACU East) to minimize contamination and selection bias by randomizing treatment and control conditions to each wing, rather than each individual subject (see Figure 1).

[figure not shown]

Figure 1. Pseudo Cluster Randomization Procedure

Patients on the unit currently receive opportunities to take part in several groups per day focused on topics of coping skills, mindfulness, journaling, creative arts, wellness recovery, recreation, and at least one music therapy group, as part of the standard of care. The current study improves upon the standard of care by providing a protocolized intervention sequence targeted at reducing internalized stigma of mental illness.

The intervention consists of a sequence of five music therapy songwriting and recording groups, one per day. Internalized stigma will be assessed within 3 days of admission (pretest/baseline), at ten days (posttest), and at 3 weeks from baseline (follow-up), using the Internalized Stigma of Mental Illness Inventory (Ritsher et al., 2003; Appendix 2).

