4.3. Study procedures

Patients will be identified and referred upon admission to the Acute Care Unit at HMH Carrier Clinic by the treatment team (attending doctors, nurses, and social workers). All subjects who are anticipated to remain admitted to the unit for at least 7 days will be considered regardless of gender or racial/ethnic background with the exception of those less than 18 years of age.

Internalized stigma will be assessed within 3 days of admission (pretest/baseline), at ten days (posttest), and at 3 weeks from baseline (follow-up), using the Internalized Stigma of Mental Illness Inventory (Ritsher et al., 2003; Appendix 2). The ISMI is a widely-used measure with acceptable internal consistency (α = .72-.90) and test–retest reliability (r = .68-.92; Boyd et al., 2014; Chang et al., 2016). It was selected over the Perceived Devaluation

and Discrimination Scale (PDD; Link, 2987) and Self-Stigma in Mental Illness Scale (SSMOI; Tucker et al., 2013) due to concerns about internal consistency and psychometric properties of these measures (Brohan et al., 2010). Data collection will include the subject's name, diagnoses, treatment ID number, and ISMI score. Treatment effect will be measured by using a two-factor, mixed-design analysis of variance (ANOVA). A P value of less than 0.05 will be considered to indicate statistical significance.

Description of Procedures

The music therapy treatment group will utilize a certified music therapist to facilitate a series of 5 group music therapy sessions over the course of 5 to 7 consecutive weekdays. Groups will be composed of 5 to 7 patients and the MT. There is no standard number of sessions for interventions addressing internalized stigma, and the available literature varies from one session in a single day to twenty sessions over a period of months. Since the average length of stay for acute care unit patients is 7 to 10 days, 5 sessions is the maximum feasible number of sessions to complete the treatment sequence for shorter stays. Though patients typically receive daily music therapy groups as part of the standard of care, this study improves upon the standard of care by providing a protocolized intervention sequence targeted at reducing internalized stigma of mental illness.

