5.4. Assignment / randomization

This prospective clinical trial's pseudo cluster randomized controlled design will take advantage of the unit's two separate residential areas ("wings") to control for contamination bias by randomizing treatment and control conditions to each wing, rather than each individual subject (see Figure 1 above).

5.5. Section of instruments (to include for all studies with a social behavioral intervention)

Internalized stigma will be assessed after enrollment, within 3 days of admission to the hospital (pretest/baseline), at ten days (posttest), and at 3 weeks after baseline (follow-up), using the Internalized Stigma of Mental Illness Inventory (Ritsher et al., 2003; Appendix 2). The ISMI is a widely-used measure with acceptable internal consistency (α = .72-.90) and test–retest reliability (r = .68-.92; Boyd et al., 2014; Chang et al., 2016). It was selected over the Perceived Devaluation and Discrimination Scale (PDD; Link, 2987) and Self-Stigma in Mental Illness Scale (SSMOI; Tucker et al., 2013) due to concerns about internal consistency and psychometric properties of these measures (Brohan et al., 2010).

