5.6. Data collection (data points, source and storage)

Data points will include the subject's name, diagnoses, and treatment ID number, to be collected from the medical chart by research staff; and ISMI score, collected from the subject by questionnaire administered by the PI. Data will be collected by research staff and entered into REDCap, a secure web application.

The participant's file as it relates to this study will only be altered by the PI, who is also the clinician implementing the intervention. After each session (and only at this time), the PI will briefly document the group topic and the patient's affect and presentation as observed. For example: "(*Participant first name*) participated in a music therapy songwriting group focused on themes of stigma and resilience. (*Participant first name*) initially presented with a blunted, flat affect, becoming more activated and brightening by the end of the session. (*He/she/they*) participated by verbally suggesting the genre '(*genre*)' and song title '(*song title*)' for the project." Documentation related to the study will not be differentiated in the participant's file from other therapeutic group activity.

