Appendix 1: Data collected

PHI: Name; DSM-5 category of diagnosis: schizophrenia spectrum and other psychotic disorders, bipolar and related disorders, depressive disorders, anxiety disorders, no diagnosis

Non-PHI: Participant ID (#); ISMI Score pre-intervention/baseline (#); ISMI Score post-intervention (#); ISMI Score 3 week follow-up (#)

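### The primary ANOVA has no term for the song groups or wing-cohorts in which MTAR is allocated and delivered, so its type I error exceeds 5% if ISMI change is positively correlated within them

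*Combined protocol and SAP*

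**What the plan says.** - **Allocation.** Section 4.1 describes "randomizing treatment and control conditions to each wing, rather than each individual subject". Section 5.4 gives the purpose: "to control for contamination bias by randomizing treatment and control conditions to each wing, rather than each individual subject". There are two wings. The text does not say whether they exchange conditions between cohorts, and Figure 1 is not available in the text reviewed.
- **Delivery.** Section 4.3: "Groups will be composed of 5 to 7 patients and the MT". Section 1 has subjects working "in groups of 5 to 7 subjects per group to compose, rehearse, and record a song". Table 4 sets out the timeline per cohort and gives controls no treatment sequence, so song groups exist only in the MTAR arm.
- **Primary outcome.** Section 3.4: "ISMI score pre-treatment, ISMI score post-treatment".
- **Primary analysis.** Section 5.8.2: "Treatment effect on the primary dependent variable (ISMI score) will be measured by using a two-factor repeated-measures analysis of variance (ANOVA"), tested at 0.05. The two factors are not named. Section 4.3 calls the same analysis a mixed design, which in ANOVA means one between-subject and one within-subject factor, not a random cluster effect.
- **Sample size.** Section 5.8.1 gives f = 0.33, alpha 0.05, 80% power, sphericity and 50 per arm. It gives no ICC, design effect, number of clusters or loss rate.
- **Data.** Appendix 1 lists, besides name and diagnostic category, "Non-PHI: Participant ID (#); ISMI Score pre-intervention/baseline (#); ISMI Score post-intervention (#); ISMI Score 3 week follow-up". Section 5.6 lists name, diagnoses "and treatment ID number, to be collected from the medical chart by research staff", and the ISMI score. Neither names wing, cohort or song group.

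**The concern.** Subjects who write and record one song together, or who share a wing at the same time, may change alike. Section 1 itself credits part of the change to mutual support within the group. An analysis of about 100 independent subjects then understates the standard error of the arm difference. The bias in the P value has a known direction: the chance of claiming that MTAR works when it does not rises above the stated 5%, and this is the trial's only primary test. The sphericity assumption in 5.8.1 does not help, because it concerns repeated measures within a subject, not correlation between subjects.

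**Working it through.** **1. The test.** Condition and time are the natural factors. With the two time points of 3.4, the arm-by-time F test equals a two-sample t-test on change (post-test minus pre-test) with 100 - 2 = 98 df and critical value 1.984. This is a reading, since 5.8.2 does not name the factors.

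**2. The plan's own figure.** Section 5.8.1 does not say which contrast f = 0.33 refers to. Read as d = 2 x 0.33 = 0.66 on change, 50 per arm gives noncentrality 0.66 x sqrt(50/2) = 3.30 and power 90%; 80% would need 76 in total. So 100 is not reproduced on this reading. That is a separate matter. The reading is used below only to price the fix.

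**3. Assumed inputs.** ICC of change 0.01, 0.05 or 0.10. Clusters per arm: 10 of 5, 8 of 6-7, or 7 of 7 (49 subjects). Control wing-cohorts are the same size as song groups. No losses. No separate wing-level effect until step 6.

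**4. Type I error of the planned test.** Design effect DE = 1 + (m - 1) x ICC. For 8 clusters, m = 50/8 = 6.25, and at ICC 0.05 DE = 1 + 5.25 x 0.05 = 1.2625.
- Both arms clustered: the true variance is 1.2625 times the assumed one. The cut-off 1.984 acts like 1.984/sqrt(1.2625) = 1.77, a two-sided error of about 8%.
- MTAR only: the ratio is (1.2625 + 1)/2 = 1.131, and the cut-off acts like 1.87, an error of about 6.5%.

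Simulation, 40,000 trials per cell (error in %, clusters per arm 10 / 8 / 7):

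| ICC (assumed) | Both arms clustered | MTAR arm only |
|---|---|---|
| 0.01 | 5.5 / 5.4 / 5.6 | 5.3 / 5.3 / 5.5 |
| 0.05 | 7.4 / 8.2 / 8.8 | 6.1 / 6.5 / 6.9 |
| 0.10 | 9.9 / 11.6 / 12.2 | 7.3 / 8.0 / 8.7 |

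**5. Tests that respect the clusters.** In the same 18 cells a t-test on cluster mean changes gives 4.9-5.2%. A random-intercept model on change, checked in the balanced layouts only, gives 3.7-4.8%. If pre-test and post-test are both kept as outcomes, a plain cluster intercept cancels from the arm-by-time contrast: in 60 simulated trials (7 of 7, ICC 0.10) the statistic stayed within 0.2% of the unadjusted t.

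**6. If each wing keeps one condition throughout.** A wing effect is then shared by all 50 subjects in an arm. For the planned test, DE = 1 + 49 x 0.01 = 1.49 at an assumed wing ICC of 0.01 and 1 + 49 x 0.05 = 3.45 at 0.05. Simulated error is about 11% and 30%. The cluster-mean t-test barely helps (about 9-10% and 24-29%), because its error term comes from variation within a wing and cannot see the wing effect.

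**7. Power of the cluster-mean t-test** (d = 0.66, df 18 / 14 / 12). Noncentrality is 0.66/sqrt(2 x DE/n), with n subjects per arm; for 8 clusters and ICC 0.05, 0.66/sqrt(2 x 1.2625/50) = 2.94 on 14 df, power 78%.

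| ICC (assumed) | Both arms, % | MTAR only, % |
|---|---|---|
| 0 | 87.7 / 86.6 / 85.0 | same |
| 0.05 | 81.3 / 78.0 / 74.9 | 84.5 / 82.2 / 79.8 |
| 0.10 | 75.1 / 70.1 / 66.0 | 81.3 / 78.0 / 74.9 |

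**The case against.** **The size is assumed throughout.** This stands. At ICC 0.01 the excess is 0.3-0.6 points, and with only MTAR clustered at 0.05 the error is 6.1-6.9%. Mutual support common to every group can raise the mean without creating variance between groups, and one clinician following a protocolized sequence may limit that variance further. Group membership still differs, and the direction is certain for any positive ICC. A reader might infer that the 5% level is known to be broken. The documents do not show that.

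**The missing IDs prove little.** This also stands in part. The data lists do not name treatment arm either, and the ANOVA cannot run without it, so the lists may not be exhaustive. A reader might infer that wing and cohort will go unrecorded; the lists cannot support that. Naming the fields is still worthwhile.

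**A wing term may be impossible.** Correct if each wing keeps one condition: the condition factor then is the wing factor. But it would be too strong to say that wing and treatment are confounded, because the text does not give the allocation schedule. It would equally be too strong to say that a cluster term restores 5% whatever the schedule.

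**Three time points may have been meant,** since sphericity is trivial with two. Section 3.4 supports two. With three, the ANOVA would still have no cluster term.

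**Conclusion.** The concern holds in conditional form. The plan allocates by wing, delivers MTAR in song groups, and tests as if subjects were independent. If ISMI change is positively correlated within song groups or wing-cohorts, the true type I error is above 5%: about 5-6%, 6-9% and 7-12% at assumed ICCs of 0.01, 0.05 and 0.10, with the lower end applying if only the MTAR arm is clustered. The omission is certain; its size is not, because it rests on the assumed ICC, cluster sizes, control cohorts and absence of losses. An analysis by cluster cures this only if wings switch condition between cohorts or there is no wing-level effect. A reader might also infer that the trial misses its 80% power. That is not shown: the power in 5.8.1 lists no allowance for clustering or loss and is unsupported on that count, no more.

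**What to change.** 1. **Section 5.8.2.** Analyse ISMI change with arm as a fixed effect, a random intercept for wing-by-cohort (the song group in the MTAR arm) and small-sample degrees of freedom such as Kenward-Roger; or use a t-test on cluster mean changes. If pre-test and post-test are both outcomes, the cluster term must be cluster-by-time. Define how controls belong to a cohort. If they have none, put the random effect in the MTAR arm only.
2. **Section 5.6 and Appendix 1.** Name wing, cohort and song-group ID as data fields.
3. **Sections 4.1 and 5.4.** State whether wings switch condition between cohorts. If each wing keeps one condition, say that treatment cannot be separated from wing by any model, and carry that limitation into the conclusion.
4. **Section 5.8.1.** Keep n = 100 and label the 80% power as assuming independent subjects.

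Cost: wording and three fields, no extra patients. For the cluster-mean test, degrees of freedom fall from 98 to 12-18. On the d = 0.66 reading with no losses, power is 85-88% at ICC 0 and 75-85% at ICC 0.05, against 90% for the unadjusted test. Because section 5.2 drops subjects who are discharged or noncompliant during treatment, these power figures are optimistic.

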Though MTAR is grounded in the research literature related to internalized stigma treatment, there are two notable divergences. First, nearly all published studies included in meta-analyses examine interventions that take place as part of outpatient treatment. While outpatient approaches may be less complicated to implement and measure, they are often remedial of internalizing stigmatizing experiences related to inpatient hospitalization. MTAR is implemented during inpatient treatment, at the critical juncture when the internalization of experiences related to hospitalization is nascent. Second, most interventions include psychoeducation as a fundamental component. Psychiatric inpatients, who typically present with a higher acuity level and may be psychotic or actively decompensating, can lack the insight for significant reflexive thinking, and can rarely self-regulate to the degree required to sit for a 60- or 90-minute psychoeducation class. For this reason, psychoeducation in this study is limited to a 10-minute introduction to the concept of internalized stigma in the first session of the treatment sequence.

A major benefit of addressing internalized stigma in an inpatient setting with music therapy is that musical experiences are intrinsically motivating and pleasurable. This stands in contrast with much of the inpatient psychiatric hospital experience, which is often characterized by isolation (Lindgren et al., 2019), feeling unsafe (Berg et al., 2017), powerlessness related to a perceived lack of influence on choice of medication and treatment (Færden et al., 2020), and feeling bored or "caged in" (Stewart et al., 2015). Music therapy is a non-threatening opportunity to take part in new experiences with new people. Combined with the acquired awareness of internalized stigma in the presence of social support, engaging in new experiences can strengthen participants' resistance to stigmatization by building internal resources based on the need for novel experiences (Szcześniak et al., 2018).

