In a peer-reviewed music therapy study that provides quantitative data that demonstrates a reduction in internalized stigma in an inpatient psychiatric setting, Silverman (2013) examines the effects of a songwriting intervention in which subjects compose lyrics for "The Stigma Blues". The study concluded that music therapy was significantly more effective in addressing internalized stigma relative to the control group, and the author suggests that the songwriting

Photovoice (Russinova et al., 2014) Characteristic	MTAR Characteristic	Rationale of Divergence
Narrow diversity of demographic characteristics in study sample/small sample size	Broad diversity of demographic characteristics at HMHCC; larger sample size	Greater generalizability of research findings

One-dimensional mode of creative expression (photography)	Multiple modes of creative expression: lyric-writing, composing, performing, and recording music.	Engaging in creative expression in various aesthetic modes offers opportunities to adapt to changing and evolving moods, perspectives, and feelings in real-time.
Parallel creative process	Collaborative creative process	Collaborating on a single work of art, rather than multiple individual works, requires a greater investment in social interaction.
Collection of individual narratives	Individual narratives integrated into a group narrative	Building a group narrative creates more opportunities for group cohesion
Peer-led	Music therapist as facilitator	MT can guide, contain, ground the sessions for higher-acuity inpatients; create meaningful opportunities by interfacing between patient and technology; occupy a supportive role in realizing group aesthetic
Outpatient	Inpatient	Prompt intervention to improve outcomes

Table 2. Comparison of Photovoice (Russinova et al., 2014) and MTAR Characteristics and Rationale of Divergence

process contributed to a disinhibition of self-disclosing personal histories of stigmatizing experiences (Silverman, 2013). MTAR includes a songwriting component, but also expands upon Silverman's approach (See Table 3).

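### Conditions go to two wings, not to patients, yet the primary model adjusts for no patient characteristic, and age, sex and prior admissions are not listed for collection

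*Combined protocol and SAP*

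**What the plan says.** Sections 4.1 and 5.4 describe a pseudo cluster design on the unit's two wings, "randomizing treatment and control conditions to each wing, rather than each individual subject". The visible text does not say how a patient comes to be on one wing or the other. Figure 1, which sets out the procedure, is not in the text available for review.

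On the primary analysis, section 5.8.2 states: "Treatment effect on the primary dependent variable (ISMI score) will be measured by using a two-factor repeated-measures analysis of variance (ANOVA". Section 4.3 calls the same analysis a mixed-design ANOVA. The two factors are presumably group and time, but neither they nor the term to be tested is written out, and no covariate is named. The hypothesis in section 3.2 concerns change from baseline relative to control.

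Diagnosis enters only a separate secondary analysis (sections 3.5, 3.6 and 5.8.2). The data lists in sections 4.3 and 5.6 and in Appendix 1 agree with one another. Appendix 1 gives the identifying items as "PHI: Name; DSM-5 category of diagnosis: schizophrenia spectrum and other psychotic disorders, bipolar and related disorders, depressive disorders, anxiety disorders, no diagnosis", and otherwise lists a participant number and three ISMI scores. Table 3 shows that demographic data here means diagnosis. Age is an eligibility limit in section 4.2.2 but is not a listed data point, and sex and prior admissions appear in no list. No comparison of the arms at baseline is planned.

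**The concern.** When patients are randomized one by one, chance balances their characteristics on average, and an unadjusted comparison is unbiased. Assigning two wings does not give that protection: whatever determines which patients are on a wing also determines who receives MTAR.

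The relevant characteristics are those that predict how ISMI moves between admission and about day ten. Diagnosis is a candidate, since the protocol plans to study how the effect varies with it. Prior admissions are another: section 2.1 argues for treating "at the critical juncture when the internalization of experiences related to hospitalization is nascent", which makes previous hospital experience a plausible predictor of change. If such a characteristic is unevenly spread over the wings, part of the between-arm difference reflects who was in each wing. The planned primary analysis has no means of separating the two, and for characteristics not recorded the report could not even show the imbalance.

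**Working it through.** **The plan's own figure.** The plan gives no figure for imbalance or bias. Its sample size is 50 per group at f = 0.33, alpha 0.05 and 80% power. A plain two-group F test at f = 0.33 needs 76 in total, and 100 gives 90% power. The number of measurements, the within-patient correlation and the dropout rate behind the 100 are not stated, so it cannot be reproduced, but it is not shown to be wrong. Nothing below depends on it except the 50 per arm.

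**Which differences bias the result.** Suppose a binary characteristic has share p1 in one wing and p0 in the other.

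- If it shifts ISMI by the same amount at pretest and post-test, it drops out of each patient's change, so the bias in group-by-time is 0. The group main effect is still biased by (p1 − p0) × shift.
- If it alters the change itself by δ, the bias in group-by-time is (p1 − p0) × δ.

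**Effect on type I error.** All gaps here are assumptions; the documents give none. SD means the SD of the change score. With 50 per arm, the noncentrality is bias / √(2/50) = 5 × bias, on 98 df, with a two-sided 5% critical value of 1.984.

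| Assumed gap in share × δ | Bias (SD) | Noncentrality | Rejection of a true null |
|---|---|---|---|
| none | 0 | 0 | 5.0% |
| 0.20 × 0.5 | 0.10 | 0.50 | 7.9% |
| 0.30 × 0.5 | 0.15 | 0.75 | 11.5% |
| 0.30 × 0.6 | 0.18 | 0.90 | 14.5% |

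If the 0.10 is instead in SDs of a single ISMI score, divide by √(2(1 − ρ)), where ρ is the pre-post correlation. At ρ = 0.5 the divisor is 1 and nothing changes. At ρ = 0.7 it is √0.6 = 0.775, so the bias is 0.129 SD of change, the noncentrality 0.645 and the rejection rate 9.8%.

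**Simulation.** This used 50 per wing, no treatment effect, ρ of 0.5 or 0.7, and a factor worth 0.5 SD of a single score, with shares of 30% against 50%.

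- Factor shifts level only: group-by-time bias 0.00 and type I error about 5%; group main effect bias 0.10 and type I error about 9%.
- Factor alters change: group-by-time bias 0.10 and type I error 7–10%.
- Factor alters change, and is entered as a main-effect covariate in the repeated-measures model: bias still about 0.10. A term that is constant over time cannot alter the difference in mean change.
- Factor alters change, and is entered as factor-by-time, or with baseline ISMI in a model of post-test ISMI: bias about 0 and type I error about 5%.

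**Degrees of freedom.** Appendix 1 has five categories, counting no diagnosis, so adjustment uses 5 − 1 = 4. The residual in the post-test model is 100 − 1 (intercept) − 1 (group) − 1 (baseline) − 4 = 93.

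**The case against.** The strongest reply is that baseline ISMI is already one of the repeated measures and the hypothesis is about change. On that reading, a wing with persistently higher stigma does no harm. This stands for the group-by-time term. A reader might infer that any case-mix difference between wings enters the treatment effect; the documents do not support that, because only predictors of change do so. The reply is incomplete because section 5.8.2 does not say which term is tested.

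Second, a reader might infer that imbalance would be invisible altogether. It would not be: diagnosis and baseline ISMI are collected and could be compared by wing at any time. Invisibility applies only to age, sex and prior admissions.

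Third, nothing shows that the wings differ. Table 4 is laid out per cohort, and groups of 5 to 7 imply about 7 to 10 treated groups for 50 patients. If conditions are re-randomized to wings across cohorts, persistent case-mix differences would tend to average out. The visible text neither confirms nor excludes this. It limits the likely size of the problem, but does not remove the value of a baseline table and prespecified adjustment.

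Fourth, the protocol expects the effect to hold regardless of diagnosis, and its secondary objective is about treatment effect by diagnosis. Neither says that diagnosis predicts untreated change. That is correct, and δ is therefore an assumption. Likewise the Table 2 entry, "Broad diversity of demographic characteristics at HMHCC; larger sample size", is background about the site, not an analysis claim.

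**Conclusion.** The point holds in limited form. Assignment by wing, a primary model with no covariate, a recorded diagnosis left out of that model, and three basic characteristics not listed for collection are all in the text. The consequence is conditional: bias arises if the wings differ in something that predicts ISMI change over the stay, or in ISMI level as well if the group main effect is what is tested.

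The size cannot be determined from the documents. The figures of 7.9% to 14.5% for type I error rest on assumed biases of 0.10 to 0.18 SD and are illustrations only. For rough scale, f = 0.33 corresponds to d = 0.66 for two groups, although section 5.8.1 does not tie f to a model term or to an SD. It would be too strong to conclude that the trial is confounded by case mix: no imbalance is documented, and the randomization figure is not available. The change is worth making because it costs little, and covariates chosen after the results are known carry less weight.

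**What to change.** In section 5.8.2, make the primary comparison post-test ISMI modelled on group, baseline ISMI and DSM-5 category, with category recorded before session 1 (and at the same point in the control wing). If the repeated-measures model is kept, name group-by-time as the tested term and include category-by-time; adding category as a main effect alone would leave the bias unchanged. Set in advance a rule for pooling sparse categories and for classifying a patient with several chart diagnoses.

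Choose between the two models beforehand, as they are not equivalent for characteristics left out. Adjustment for baseline ISMI alone removes most, but not all, of a stable level difference: in the simulation with ρ = 0.7 and shares of 30% against 50%, about 0.03 SD remained.

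In section 5.6 and Appendix 1, add age, sex and number of prior psychiatric admissions from the chart. Tabulate these, diagnosis and baseline ISMI by arm. Pre-state one sensitivity analysis of the primary comparison that adjusts for the three in the same way.

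The cost is up to 4 degrees of freedom, three chart fields per subject (the chart is already opened for diagnosis) and a small amendment, with no added patient contact. None of this removes differences in how the two wings are run.
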